
The objective of this trial is to provide 6 months of safety follow-up for children and adolescents with dilutional (euvoletic or hypervolemic) hyponatremia who have previously participated in a tolvaptan hyponatremia trial, and to assess the efficacy of tolvaptan in increasing serum sodium for those subjects who receive optional continuing tolvaptan treatment of variable duration (up to 6 months).

Core Safety Follow-up Component

- For all subjects: To evaluate the post-treatment safety follow-up of children and adolescent subjects with dilutional (euvoletic or hypervolemic) hyponatremia who have previously participated in a tolvaptan hyponatremia trial.

Optional Tolvaptan Treatment Component

- For subjects who receive optional tolvaptan treatment: To demonstrate that tolvaptan safely and effectively achieves and maintains increased serum sodium concentrations in children and adolescent subjects with dilutional (euvoletic or hypervolemic) hyponatremia when used for both multiple short-term treatments, and/or longer chronic treatments.

3 Trial Design

This trial consists of 2 components, a 6-month safety follow-up trial, and an embedded optional tolvaptan treatment trial for eligible subjects.

Core Safety Follow-up Component

The core safety follow-up component of the trial is a 6-month period in which pediatric subjects (children and adolescents) with dilutional (euvoletic or hypervolemic) hyponatremia who previously participated in a tolvaptan hyponatremia trial will be followed (at a clinical trial site and/or through telephone calls), regardless of the need for treatment for hyponatremia, to assess the long-term safety of tolvaptan. There is no screening phase.

Enrollment into this trial should follow completion or discontinuation from the previous tolvaptan hyponatremia trial; the subject must have been off investigational medicinal product (IMP) for at least 7 days between trials. A longer lapse between completion of the previous tolvaptan hyponatremia trial and enrollment into this trial is permitted while enrollment is open.

The final laboratory assessments for liver function tests (LFTs) from the previous tolvaptan trial can serve as the baseline laboratory assessments for this trial if the values are within the normal range, and collected within 30 days of the baseline visit for this trial. However, LFTs for these subjects will be collected at Month 1 or Month 2 at a clinical site visit or local laboratory. If LFTs from the previous tolvaptan trial are abnormal, or collected > 30 days of the baseline visit of this trial, they will be assessed at baseline.

The last assessments in the previous tolvaptan trial will serve as the baseline assessments if collected within 30 days of enrollment into this trial. Otherwise, assessments will be repeated if > 30 days have lapsed since the previous tolvaptan trial.

Subjects enrolled in this trial will be assessed up to 7 times over the 6-month core safety follow-up component of the trial. The baseline and the Month 6/Early Termination (ET) visits are performed in the clinic, while assessments during Months 1, 2, 3, 4 and 5 will be conducted by telephone, unless LFTs are required at Month 1 or Month 2. During the in-clinic visits, subjects are evaluated for relevant trial information.

Baseline Visit

All subjects will attend the clinic for the baseline visit.

Months 1, 2, 3, 4 and 5

All subjects will receive telephone assessments for Months 1, 2, 3, 4, and 5. If LFTs are required at Month 1 or Month 2, the subject may obtain these results through a clinic visit or from a local laboratory.

Month 6/End of Trial Visit

All subjects will attend the clinic for the Month 6/End of Trial visit.

Optional Tolvaptan Treatment Component

Subjects enrolled in the 6-month core safety follow-up component may be eligible to receive optional tolvaptan treatment for their hyponatremia. Eligibility for optional tolvaptan treatment must be determined at the pre-treatment baseline visit (Day -4 to Day 1) of each dosing cycle. Eligible subjects can be treated at any time with optional

tolvaptan during the 6-month core safety follow-up component. Optional tolvaptan treatment duration will be case-specific; it can be short-term or long-term, and consist of 1 or more treatment cycles. When a cycle with optional tolvaptan treatment is completed, including the Follow-up Phase visits, subjects will continue in the core safety component to complete the remainder of visits until Month 6. Within this trial, tolvaptan treatment will not extend beyond the 6-month core safety trial period. If the subject completes the 6-month core safety component while on optional tolvaptan treatment, the subject will complete the Month 6 core safety component visit, terminate treatment, and immediately enter the Follow-up Phase.

If a subject simultaneously participates in both core safety and optional tolvaptan treatment components, the visit days will be calculated between both components to ensure the assessments can be overlapped, where applicable.

Thirty days after the start of optional tolvaptan treatment, subjects will interrupt treatment for up to 2 doses (Days 31-32). The need for continuing treatment after this tolvaptan interruption will be assessed at minimum once daily (or more as needed) during this time.

Subjects who are expected to receive tolvaptan for greater than 30 days duration should demonstrate the need for continued treatment by discontinuing tolvaptan for up to 2 consecutive doses while undergoing close monitoring of serum sodium levels.

However, there is a subgroup of subjects who have an identifiable cause for hyponatremia that has not (or cannot be) changed that will have an option to be excused from this brief interruption of tolvaptan. Examples of such causes include concomitant treatment for refractory seizures with a hyponatremia-inducing medication such as oxcarbazepine (which can increase vasopressin production by the pituitary) that cannot be changed or discontinued, or subjects with a known underlying hyponatremia inducing condition such as volume overload from a failing Fontan repair.

The optional tolvaptan treatment component of the trial will be available for the 6-month duration of the core safety component for each subject.

4 Sample Size and Power Justification

Sample size was not determined by a formal computation to achieve a target power. It is expected that approximately 100 subjects may enroll from previous tolvaptan pediatric trials for hyponatremia

5 Statistical Methods

5.1 Efficacy Analysis

Due to the early termination status, not all planned analyses will be provided due to lack of data. For an example, no subject received optional Tolvaptan treatment, the efficacy analyses specified in the SAP will not be applied to Optional Tolvaptan Treatment Component.

5.1.1 Data Sets Analyzed

The following datasets are defined for this trial:

- Enrolled Subjects (core safety follow-up component)
 - Core Dataset: comprises all subjects for whom an ICF is signed for the trial.
- Treated Subjects (optional tolvaptan treatment component)
 - Safety Dataset: comprises those subjects who receive at least one dose of tolvaptan.
 - Efficacy Dataset: comprises those subjects in the safety dataset who have at least one post-baseline efficacy evaluation for serum sodium concentration.

5.1.2 Handling of Missing Data

The primary dataset for efficacy analyses will be the observed cases (OC) dataset. The OC dataset will consist of the actual observations recorded at each visit so that no imputation of missing values will be made.

5.1.3 Baseline Characteristics and Baseline Comparability

Demographic characteristics and medical history at baseline will be summarized by descriptive statistics, e.g., proportion, mean, median, standard deviation(SD), minimum and maximum values.

Baseline characteristics by age categories (≥ 4 weeks to < 4 years, ≥ 4 years to < 8 years, ≥ 8 years to < 12 years, ≥ 12 years to < 18 years) will also be provided. Baseline characteristics by underlying etiology (heart failure, hepatocellular disease, syndrome of inappropriate antidiuretic hormone secretion (SIADH) or other diseases) will be provided as well.

5.1.4 Treatment Compliance

For subjects participating in the Optional Tolvaptan Treatment Component, treatment compliance will be calculated for each cycle by dividing the total dosage taken during the cycle by the total dosage the subjects are scheduled to take during the cycle based on the Study Medication panel of the case report form (CRF). The overall treatment compliance across cycles will be provided

5.1.5 Protocol Deviations

Protocol deviations data will be summarized by type of deviations (e.g., deviations in entry criteria, dosing, concomitant medication, procedural, etc.) by center and treatment group. In addition, a subject listing will be provided describing the deviations for each subject.

5.1.6 Primary Outcome Analyses

5.1.6.1 Analysis of Primary Outcome Endpoint

The primary endpoint for all subjects participating in the Optional Tolvaptan Treatment Component of the trial is change from baseline in serum sodium while tolvaptan is being administered. The descriptive statistics will be provided for the primary endpoint.

The primary endpoint will be analyzed by age groups (≥ 4 weeks to < 4 years, ≥ 4 years to < 8 years, ≥ 8 years to < 12 years, ≥ 12 years to < 18 years).

5.1.6.2 Technical Computational Details for Primary Outcome Analysis

- 1) Baseline for the primary endpoint is the last evaluation of serum sodium prior to the first dose at each cycle in the Optional Tolvaptan Treatment Component.
- 2) For safety purpose, additional unscheduled serum sodium between scheduled efficacy endpoints may be collected measured in the local hospital labs. These assessments of serum sodium will not be included in the primary efficacy analysis.
- 3) The primary analysis will be only performed on the Optional Treatment Efficacy Sample.

5.1.7 Secondary Outcome Analysis

5.1.7.1 Analyses of Secondary Outcome Variables

The secondary endpoints for all subjects receiving tolvaptan in the Optional Tolvaptan Treatment Component of the trial include the following:

- Percentage of subjects who require rescue therapy while on tolvaptan
- Percentage of subjects who have recurrence of hyponatremia while on tolvaptan

- Percentage of subjects requiring continuation of tolvaptan following 30 days of treatment
- Percentage of subjects with overly rapid correction in serum sodium (≥ 12 mEq/L [mmol/L]) in 24 hours after the first dose at introduction or reintroduction of tolvaptan
- Changes from baseline in ALT, AST, BT and creatinine for subjects on tolvaptan

The secondary endpoints for subjects participating in the Core Safety Follow-up Component of the trial include:

- Frequency of AE reports
- Change from baseline in QoL assessments
- Change from baseline in growth percentiles by visit for body height and weight
- Tanner Staging progression score (at 6 months)

All secondary endpoints will be summarized using descriptive statistics.

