3.5.2.2 Safety Variables

Safety variables listed below and their differences from baseline will be summarized.

The safety variables are the following:

- Frequency of AE reports (including cases of dehydration)
- Changes from baseline in growth percentiles by visit for body height and weight
- Tanner Staging progression score (at 6 months)

In addition to the safety variables reported for all subjects, the following variables will be assessed for subjects who enter the optional tolvaptan treatment component of the trial:

- Percentage of subjects with overly rapid correction in serum sodium (≥ 12 mEq/L ([mmol/L]) in 24 hours after the first dose at introduction or reintroduction of tolvaptan)
- Changes from baseline in ALT, AST, BT and creatinine for subjects on tolvaptan

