- 9) Body height and body weight will be measured.
- 10) Growth percentile will be calculated. Prior growth development information should also be collected, if available.

- 11) Tanner Staging will be transferred from the last assessments from the previous trial or completed as part of the physical examination, as appropriate. Historical staging information should also be collected, if available. A subject who has reached Stage 5 (both in pubic hair and genitalia) does not need to continue with Tanner Staging.
- 12) If the subject's last LFT (AST, ALT or BT) was abnormal or the subject's baseline visit occurred > 30 days after completion of the previous trial, the subject will be required to have LFTs assessed at baseline. If the subject's last LFTs were normal and the baseline visit occurred < 30 days after completion of the previous trial, LFTs will be collected at Month 1 or Month 2.
- 13) Quality of Life assessment will be performed, as appropriate by age and where available.
- 14) Concomitant medications will be recorded. If > 30 days have lapsed since the previous tolvaptan trial, medications taken within 30 days of enrollment will be recorded.
- 15) Adverse events will be assessed.

3.7.3.1.2 Months 1, 2, 3, 4, and 5

Subjects and/or their parents or legal guardians will be contacted by telephone at the end of Months 1, 2, 3, 4, and 5 (+ 2 weeks) to assess any new or ongoing AEs and to collect information on any medications administered since the last visit.

If the subject's last LFTs were normal and the baseline visit occurred < 30 days after completion of the previous trial, LFTs will be collected at Month 1 or Month 2 (in-clinic visit or local laboratory).

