3.7.3.1.3 Month 6/Early Termination

Subjects will return to the clinical trial site at the end of Month 6 (+ 2 weeks) or at early termination (ET) and the following assessments will be performed:

- 1) Any observable symptoms of hyponatremia will be assessed and recorded separately.
- 2) Vital signs (blood pressure, heart rate, respiratory rate, and temperature) will be assessed after the subject has been supine for ≥ 3 minutes. Vital signs should be performed prior to any blood draws.
- 3) A directed physical examination will be performed. Physical examination should include a fontanelle assessment as age appropriate.
- 4) Body height will be measured.
- 5) Body weight will be measured.
- 6) Growth percentile will be calculated.

- 7) Tanner Staging will be completed at the Month 6 clinical trial site visit or at ET according to the instructions specified in [Section 3.7.5.6](#) and [Appendix 4](#). A subject who has reached Stage 5 (both in pubic hair and genitalia) does not need to continue with Tanner Staging.
- 8) Quality of Life assessment will be performed, as appropriate by age and where available.
- 9) Concomitant medications will be recorded.
- 10) Adverse events will be assessed.

Month 6 is the completion visit, and subjects will no longer be eligible for optional tolvaptan treatment under this protocol at this time.

If a subject terminates early from the trial and agrees to continued telephone contact, the subject or parent/legal guardian will be contacted by telephone at Month 6 to assess vital status.

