5.1.7.2 Technical Computational Details for the Analysis of the Secondary Endpoints

- 1) Baseline for the continuous secondary endpoints of the subjects receiving tolvaptan in the Optional Tolvaptan Treatment Component is the last evaluation prior to the first dose at each cycle in the Optional Tolvaptan Treatment Component. This applies to ALT, AST and BT.
- 2) Baseline for the continuous secondary endpoints except QoL and serum sodium of the subjects participating in the Core Safety Follow-up Component is the last evaluations from the previous trial, if the last evaluation was done in previous trials within one month of this trial starts. If more than one month passes between trials, the baseline will be the evaluations at the baseline visit of this trial.
The baseline for QoL and serum sodium of the subjects in the Core Safety Follow-up Component is the evaluations at the baseline visit.
- 3) The QoL assessment includes the PedsQL Generic Core Scale (QoL GCS) and PedsQL Multidimensional Fatigue Scale (QoL MFS). For the QoL GCS, the change from baseline in QoL GCS total score, physical health summary score, and psychosocial health summary score will be analyzed using the descriptive statistics. For the QoL MFS, the QoL MFS total score will be analyzed using the descriptive statistics.
- 4) The QoL GCS scale consists of 23 items encompassing physical, emotional, social, and school domains.
For ease of interpretability, items are reversed scored and linearly transformed to a 0-100 scale, so that higher scores indicate better HRQOL (Health-Related Quality of Life).

To reverse score, transform the 0-4 scale items to 0-100 as follows: 0 = 100, 1 = 75, 2 = 50, 3 = 25, 4 = 0.

To create scale scores, the mean is computed as the sum of the items divided by the number of items answered (this accounts for missing data). If more than 50% of the items in the scale are missing, the scale scores should not be computed. If 50% or more items are completed, then impute missing scores by the mean of the completed items in a scale.

To create the Psychosocial Health Summary Score, the mean is computed as the sum of the items divided by the number of items answered in the Emotional, Social, and School Functioning Scales. The Physical Health Summary Score is the same as the Physical Functioning Scale Score.

To create the total scale score, the mean is computed as the sum of all the items divided by the number of items answered on all the scales.

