5.2 Safety Analysis

Due to the early termination status, not all planned safety analyses will be provided due to lack of data. For an example, no subject received optional Tolvaptan treatment, the safety analyses specified in the SAP will not be applied to Optional Tolvaptan Treatment Component.

Safety variables to be analyzed include adverse events (AEs), clinical laboratory data, and vital signs. In general, summary statistics will be provided for safety variables based on all available data.

Baseline of the subjects receiving tolvaptan in the Optional Tolvaptan Treatment Component is the last evaluation prior to the first dose at each cycle in the Optional Tolvaptan Treatment Component. Baseline of the subjects participating in the Core Safety Follow-up Component is the last evaluations from the previous trial (tolvaptan in Trial 156-08-276), if the last evaluation was done in previous trials within one month of this trial starts. If more than one month passes between trials, the baseline will be the evaluations at the baseline visit of this trial.

Safety analyses by age categories (≥ 4 weeks to < 4 years, ≥ 4 years to < 8 years, ≥ 8 years to < 12 years, ≥ 12 years to < 18 years) will be provided. Safety analysis by underlying etiology (heart failure, hepatocellular disease, SIADH/other) will also be provided.

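### Growth is summarised only as change in percentile, so the same growth loss counts differently depending on where a child starts

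*SAP*

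**What the plan says.** The SAP lists among the secondary endpoints of the core safety follow-up component "Change from baseline in growth percentiles by visit for body height and weight" (5.1.7.1). Protocol 3.5.2.2 gives the same endpoint as a safety variable, "Changes from baseline in growth percentiles by visit for body height and weight", and Protocol 7.4.2 repeats it for all enrolled subjects. The planned analysis is one sentence: "All secondary endpoints will be summarized using descriptive statistics".

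Height and weight are measured in clinic at the two core visits. At baseline, Protocol 3.7.3.1.1 then says "Growth percentile will be calculated. Prior growth development information should also be collected, if available". At Month 6 or early termination, Protocol 3.7.3.1.3 says "Growth percentile will be calculated". The contacts between those visits are by telephone, so the core schedule gives essentially one change value per child for each measure.

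SAP 5.1.7.2 sets item-level scoring rules for quality of life, but for growth it gives only the general baseline rule: "Baseline for the continuous secondary endpoints except QoL and serum sodium of the subjects participating in the Core Safety Follow-up Component is the last evaluations" of the previous trial when those are recent enough, and otherwise the baseline visit. No z-score, transformation or growth reference is specified for the endpoint. Protocol 2.2 does cite growth charts, but only to support a typical weight at age 6 in the dosing rationale.

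**The concern.** A percentile is a rank in a reference population. Near the median a small change in size moves a child past many others. In either tail the same change moves the child past very few. A mean of percentile changes therefore weights children near the median heavily and children in the tails lightly, although each may have lost the same amount of growth relative to age and sex. The SD has a related problem: it mixes real variation in growth with variation in starting position.

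At stake is whether the growth table can be read. If a cohort is mostly small for age, a real loss appears as a modest mean. SAP 5.2 also plans subgroup summaries: "Safety analysis by underlying etiology (heart failure, hepatocellular disease, SIADH/other) will also be provided". If growth is included in them, groups that differ in baseline size would show different mean percentile changes for the same growth loss.

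**Working it through.** **Nothing to reproduce.** The plan gives no effect size, SD or power for growth; SAP section 4 states "Sample size was not determined by a formal computation to achieve a target power". The check is therefore on how the scale behaves.

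**Inputs.** From the documents: the endpoint is change in percentile, summarised descriptively. Assumed, because the documents do not supply them: z is about standard normal in the growth reference; the loss d is 0.25, 0.5 or 1.0 SD, as illustrations; the baseline z0 ranges from -3 to +2.

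**Step 1, one child.** With percentile = 100 × Φ(z), a loss of d SD from z0 gives a change of 100 × [Φ(z0 - d) - Φ(z0)]. For d = 0.5:

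- z0 = 0: 30.85 - 50.00 = -19.1 points
- z0 = -1: 6.68 - 15.87 = -9.2 points
- z0 = -2: 0.62 - 2.28 = -1.65 points
- z0 = +2: 93.32 - 97.72 = -4.4 points

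The median-to-z = -2 ratio is 19.146 / 1.654 = 11.6. On the z scale all four changes are -0.50.

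**Step 2, other sizes of loss.** The pattern does not depend on choosing 0.5 SD:

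| Loss | z0 = 0 | z0 = -1 | z0 = -2 | z0 = -3 |
|---|---|---|---|---|
| 0.25 SD | -9.9 | -5.3 | -1.05 | -0.08 |
| 0.5 SD | -19.1 | -9.2 | -1.65 | -0.11 |
| 1.0 SD | -34.1 | -13.6 | -2.1 | -0.13 |

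**Step 3, the cohort mean, which is what the SAP would report.** Suppose every child loses 0.5 SD and baseline z follows N(μ, 1). Averaging Step 1 over that distribution gives 100 × [Φ((μ - 0.5)/√2) - Φ(μ/√2)]:

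- μ = 0: -13.8 points
- μ = -1: -9.5 points
- μ = -1.5: -6.6 points
- μ = -2: -4.0 points

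The mean z change is -0.50 in each case. Between μ = 0 and μ = -2 the reported mean differs by a factor of 13.8 / 4.0 = 3.4 for the same growth loss.

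**Step 4, mixed changes.** Take one child at the median who gains 0.1 SD (+4.0 points) and one at z = -2 who loses 0.5 SD (-1.65 points). The mean percentile change is (3.98 - 1.65)/2 = +1.2 points, while the mean z change is (0.1 - 0.5)/2 = -0.2. The two summaries differ in sign.

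**The case against.** The strongest reply is that little depends on this scale. Growth is one of several secondary endpoints, with no test, threshold, power target or control group. The SAP states that the trial terminated early and that no subject received optional tolvaptan, so any growth change seen is uncontrolled follow-up after an earlier trial. Percentile change is also the protocol's own endpoint, which the SAP follows, and z-scores can be derived later from the measured height and weight. All of this stands and limits the weight of the point. It does not remove it: SAP 5.1 and 5.2 drop the optional-treatment analyses, while growth is listed for the core component. Reporting the median, minimum and maximum would not undo the compression.

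A reader might also infer four stronger things that the documents do not support:

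- **That these children are known to sit in the lower tail.** Heart failure and hepatocellular disease make that plausible, but no baseline percentile is given, and SIADH/other is also an etiology group.
- **That the mean would look close to zero despite a general loss.** For a uniform 0.5 SD loss it is still -4.0 points with baseline z centred at -2. A near-zero mean needs a more extreme cohort or offsetting gains, as in Step 4.
- **That the problem concerns young children.** It concerns children who are small for their age and, in the upper tail, large for their age.
- **That the core component exists chiefly to detect developmental harm.** The stated objective is post-treatment safety follow-up, with growth one variable beside adverse events and Tanner staging.

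**Conclusion.** The point holds as a limitation of the planned summary. Change in percentile does not weight equal growth loss equally: the same 0.5 SD loss counts about 12 times less at z = -2 than at the median, and the upper tail is compressed too. For a uniform loss, the cohort mean shrinks from -13.8 to -4.0 points as the centre of baseline z moves from 0 to -2.

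These figures rest on a standard normal z in the reference, an illustrative loss that the documents neither state nor call clinically relevant, and an unverified distribution of baseline size. SAP 5.2 names adverse events, laboratory data and vital signs as the safety variables, so whether growth would be tabulated by etiology is not explicit. Distortion of those comparisons is conditional on that, and on the groups differing in baseline size.

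The consequence is a growth summary that may mask or distort a loss. No error rate or decision rule is affected. The point merits a change because the remedy is cheap, not because the defect threatens the trial's conclusions.

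**What to change.** In SAP 5.1.7.1 and 5.1.7.2, name an age- and sex-specific growth reference. None is tied to the endpoint now, so this must come first. Derive height-for-age and weight-for-age z-scores from the measured height and weight, keeping the existing baseline rule, and summarise change from baseline in z-score with the same descriptive statistics. Keep the percentile summary so that the protocol endpoint is still reported.

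No new visits or measurements are needed. The cost is one derivation rule and one extra table. Naming the reference also makes the percentile summary itself reproducible.
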